## *Study outcomes*

Primary retention outcomes: 1) Proportion of patients retained in care at 6-months; (2) visit attendance; and 3) VL (suppressed = HIV RNA < 400 copies). Primary workload outcome is cumulative B2C referrals at 6 months. Secondary outcomes include: Text response rates, #visit date change requests, #ART outcomes updated, % of failed messages, client contact number updates, % referral of true LTFU for tracing, and B2C tracing outcomes (transfer, stop, alive, etc.).

Table: Outcomes	Definition	Source	Phase	
Individual level (Reach and Effectiveness):			R21	R33
Retention outcomes				
Retention	6-month ART retention (alive on ART or client report of transferred care)	EMRS	X	X
ART visit adherence	% of visits attended		X	X
Viral load	% suppressed (HIV RNA <400 copies)			
Workload outcome:				
Healthcare workload	# cumulative B2C referrals at 6 months; time spent on 2WT and B2C	Time-motion, EMRS, 2WT database	X	X

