## *Sample size calculation*

Supposing a two-arm prospective study with 3-4 months recruitment period and 6 months follow-up. Assume the hazard for the control group is a constant risk over time at 0.2 (20%). To achieve 80% power to detect a hazard ratio of 0.41 in the exposed group by using a two-sided 0.05-level log-rank test, the required sample size per arm is 197. With an estimated dropout of 10%, 410 (205 per arm) will be needed, and up to 500 will be enrolled, total, to allow for buffer and withdrawal of those with lack of SMS confirmation receipt (documented).).

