### *Data analysis*

#### *Retention:*

Descriptive statistics will be performed to explore the patients' characteristics at ART initiation using means or medians for continuous variables and proportions for categorical variables. Chi-square test and Kruskal-Wallis tests will be used to compare baseline characteristics. The proportion of patients retained in ART care (or known transferred in care) at 6 and 12 months post-ART initiation between groups using chi-square test will be compared, reporting relative risks and 95% confidence intervals (CIs). Time to event analysis will explore retention curves between groups in the first year of ART. T-test will compare the mean proportion of attended ART visits between groups. VL suppression (HIV RNA < 400 copies) at 12 months post-ART initiation will be compared between groups using chi-square test, reporting relative risks and 95% CIs. Multivariate logistic regression models (12-month retention v not) will quantify the magnitude of retention difference between groups, adjusting for any potential confounders (age, sex, WHO stage at ART initiation, etc.). Statistical analysis: B2C referrals (workload) outcomes: T-test will compare the cumulative number of B2C referrals between groups. A multivariate linear regression model will further quantify the effect of intervention on referrals, adjusting for potential confounders. For the RCT, the above outcomes will be measured and compared between arms at 6 months.

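### Four outcomes are called primary and each gets its own unadjusted test, with no lead outcome, order or success rule; if any one significant result counted as success, the false positive risk would be about 13–17% at assumed correlations of 0.7 to 0.3

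*Combined protocol and SAP*

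**What the plan says.** The Study outcomes section sets out two groups of primary outcomes. The first has three members: "Primary retention outcomes: 1) Proportion of patients retained in care at 6-months; (2) visit attendance; and 3) VL". The second has one: "Primary workload outcome is cumulative B2C referrals at 6 months". The retention outcomes are numbered 1 to 3, but nothing says that the numbers are a testing order, and referrals lie outside the numbering.

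The Data analysis section assigns one test to each:

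- Retention: chi-square, with a relative risk and 95% confidence interval.
- Visit attendance: "T-test will compare the mean proportion of attended ART visits between groups".
- Viral load suppression: "will be compared between groups using chi-square test, reporting relative risks and 95% CIs".
- Referrals: "T-test will compare the cumulative number of B2C referrals between groups".

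Much of that section describes 12-month comparisons, but its last sentence moves the RCT comparison of all these outcomes to 6 months. It gives no significance level. The only level in the plan is in the Sample size calculation section: "by using a two-sided 0.05-level log-rank test, the required sample size per arm is 197". That section sizes one comparison and does not say what event it counts.

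No section gives a lead outcome, a hierarchy, a division of alpha, a multiplicity correction or a rule for overall success.

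**The concern.** With four outcomes of equal standing and no rule, the choice of what counts as a positive trial can be made after the results are known. A significant difference in attendance alone, with no difference in retention, could be presented as a positive primary result and nothing in the plan would contradict it. The 5% error rate of a single test would then not apply to the overall claim.

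This matters because of why the trial is being run. The Executive Summary and the Overall approach section say that the Ministry of Health asked for stronger evidence of impact, and the results are meant to inform scale-up. The plan also states one power figure, 80%, which a reader could take to cover all the primary outcomes. It was calculated for one comparison only.

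**Working it through.** **Inputs from the plan.** Four primary outcomes (Study outcomes). One unadjusted test each, compared at 6 months (Data analysis). Two-sided 0.05, 80% power, hazard ratio 0.41, 197 per arm (Sample size calculation).

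**Inputs assumed.** Each test is at two-sided 0.05. This is inferred from the sample size section and from the 95% intervals for the two binary outcomes. There is no true effect on any outcome. The test statistics are jointly normal with one common pairwise correlation, set at 0.3, 0.5 or 0.7 because the plan gives no figure.

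**The plan's own figure.** It states no overall error rate, so there is none to reproduce. For the sample size, the Schoenfeld formula gives 4 × (1.960 + 0.842)² / (ln 0.41)² = 4 × 7.85 / 0.795 = 39.5, so 40 events. If 20% is the control risk by 6 months, the 2wT risk is 1 − 0.8^0.41 = 8.7%, and n per arm = 40 / (0.200 + 0.087) = 140. The Freedman formula gives 45 events and 157 per arm. Values near 197 appear only under particular choices of time unit and accrual that the section does not state. The figure of 197 can therefore be neither confirmed nor called wrong, and nothing below on the error rate depends on it.

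**Chance of at least one false positive.**

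- Four independent tests: 1 − 0.95⁴ = 18.5%.
- Three independent tests: 1 − 0.95³ = 14.3%.
- Correlated tests, by simulation of one million or more draws:

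| Common correlation (assumed) | Four tests | Three tests |
|---|---|---|
| 0 | 18.5% | 14.3% |
| 0.3 | 17.4% | 13.6% |
| 0.5 | 15.6% | 12.5% |
| 0.7 | 13.0% | 10.9% |

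Counting only false claims in favour of 2wT, four tests give 1 − 0.975⁴ = 9.6% under independence and 6.5% at correlation 0.7, against 2.5% for a single test.

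**Why the three-test column matters.** The Routine ART initiation procedures section schedules viral load at initiation and then annually. The Data analysis section first places the viral load comparison at 12 months, then moves all RCT comparisons to 6 months. If routine viral load is not available at 6 months, only three primary outcomes can be tested.

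**What splitting alpha would cost retention.** A four-way Bonferroni split (0.0125 each) raises the Schoenfeld requirement from 40 to 57 events, about 42% more; with 40 events, power falls from 80% to 63%. A two-outcome Holm procedure tests retention at 0.025 in its stricter case: 4 × (2.241 + 0.842)² / 0.795 = 47.8, so 48 events, and power with 40 events is Φ(√40 × 0.892/2 − 2.241) = 72%.

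**The case against.** The strongest case on the other side has four parts.

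*The plan does not adopt an any-of-four rule.* This stands. The plan is silent, and the Study Objectives speak of raising retention and reducing tracing work together. A reader might infer that the protocol permits success on any single outcome, or that it requires both aims to be met. It states neither, so the error rates above are conditional on the first reading. The silence is itself the weakness.

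*Retention and workload are separate questions.* This stands in part. If they are two claims, the workload claim has one test at 5%. The retention claim still has three, giving 14.3% under independence and 10.9% at correlation 0.7. Separating the domains reduces the problem but does not remove it.

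*18.5% overstates the risk.* This stands. It is the value under independence, and these outcomes are unlikely to be independent: in the control and intervention procedures, a visit missed by 14 days both marks a client as lost and triggers referral, and missed visits also lower attendance. The 13–17% range is the better guide, although its correlations are assumed and taken as equal for all pairs.

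*Retention is the outcome the trial was sized for.* It is tempting to say that 80% power applies to retention and to nothing else. The documents do not quite support that. The calculation is for a log-rank test with an unnamed event, whereas primary retention is a proportion tested by chi-square. Loss from care is the event that fits a hazard ratio over 6 months of follow-up, but that is an inference. It is plain that nothing was sized for attendance, viral load or referrals.

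**Conclusion.** The point holds in a limited form. Four outcomes are labelled primary, each has its own unadjusted test, and no section says which leads or what makes the trial positive. If any one significant result were reported as a positive primary result, the chance of at least one false positive would be about 13–17% at correlations of 0.7 to 0.3, and 18.5% under independence. With viral load unavailable at 6 months it would be about 11–14%. These figures rest on an implied 5% level per test, no true effect on any outcome, and assumed common correlations.

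The documents do not support saying that the trial has an 18.5% error rate, or that it plans to claim success on any one of four outcomes. They do support saying that nothing in the plan prevents such a claim. This should be settled in writing before the analysis; it does not call the design or the data collection into question.

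**What to change.** In the Study outcomes section, name 6-month retention as the single primary outcome, tested at two-sided 5%. This agrees with the broad objective, where retention is the lead aim, and with the 82% retention target under Limitations and uncertainties. Make cumulative B2C referrals the key secondary outcome, tested at 5% only if retention is significant. Report visit attendance and viral load as secondary, with 95% confidence intervals and no separate claim of success. Repeat the order and the significance level in the Data analysis section, and state in the Sample size calculation section which event the log-rank test counts.

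This is a change of wording only, and retention keeps the full 5%, so it loses no power. The cost falls on workload, which is a stated objective. The Background describes ways in which 2wT could cut referrals without changing true retention, such as moving a visit date or recording an outcome before day 14. Under this order, a fall in referrals could not be claimed as confirmed if retention showed no difference.

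If the sponsor wants workload to stand as its own claim, keep retention and referrals as two co-primaries with Holm adjustment. In the stricter case retention is then tested at 2.5%, which needs 48 events rather than 40 for 80% power. Whether 197 per arm supplies them depends on the unstated time unit of the 0.2 hazard. If 20% is the 6-month control risk, about 197 × 0.287 = 57 events would be expected, which is enough for the log-rank comparison; under a slower hazard it might not be.

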## *Participant eligibility*

The intervention will be offered to all new ART registrants and new ART initiates (clients who initiated ART in the last 6 months) at MPC and LH aged 18 years and above with mobile phones. This allows for collection of all outcome data by 12 months. 2WT-specific eligibility criteria for all clients are: 1) New ART registrants (Initial screening visit for ART initiation) OR new ART initiate (within 6 months of initiating ART); 2)  $\geq 18$  years; 3) possession of own phone at enrollment; 4) willing to receive/send SMS; 5) informed consent; 6) receives confirmed 2WT enrollment text to verify enrollment number; and 7) initiates ART. Those without cell phones will

be excluded. As phone sharing is common, informed 2WT-specific consent will ascertain whether eligible clients have consistent access to send and receive messages. Patients will see example text context that will not contain HIV- or clinic-based information to reduce risk of disclosure; these steps have been used in similar SMS-based studies [72, 73]. 2WT cannot control message content sent by clients. Study-eligible clients will be automatically enrolled into 2wT messages with confirmed ART dispensing. Consenting 2wT enrollees who do not initiate ART will not be sent messages.

#### *Recruitment of 2wT clients:*

Information about the study will be disseminated through MPC teams. As the backbone of the intervention, the Back to Care program is already part of the core patient counseling for ART registrants, taking place before ART initiation. Adding the study-specific information will occur during this routine part of ART initiation counseling, while clients are considered *ART registrants*. Over 92% of ART registrants initiate ART the same day. Recruitment will be managed by a specifically-trained research coordinator who will be a part of the Back to Care program. This research coordinator will meet with incoming ART initiation patients to sensitize them about the opportunity to participate in a study of text-based follow-up; those meeting eligibility criteria will be informed as a group about the opportunity to participate in the study. Flyers will also be available in clinic waiting areas and counseling rooms. Interested patients at ART initiation visit or within 6 months of ART initiation will be referred to the study staff for study enrollment and informed consent. Participant enrollment may be made by teams/clinicians using the Medic Mobile phone/tablet app or the laptop-based system.

#### *Randomization*

After routine recruitment consistent with 2wT procedures, eligibility, and informed consent, 410 2wT-eligible participants will be randomized 1:1 intervention and control using a randomized block design in groups of 10. Assignments will be held in opaque envelopes distributed to LH and MPC to meet enrollment pace. This block design reduces variability within treatment conditions and potential confounding, allowing near equal-size groups for interim analysis. Site coordinator will be unaware of the envelope's contents until the participant opened and revealed the group assignment to the coordinator. Coordinator then enters participant group assignment as part of 2wT enrolment, confirming phone number as is routine. Those who do not receive the confirmation text while in clinic will be immediately withdrawn and replaced. The study design requires that participants and clinic staff are aware of allocation after assignment as routine early retention and B2C processes differ from 2wT.

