## *Staff training*

All staff at LH and MPC will be informed of the study and briefed on study protocols. A 2WT study coordinator, selected from current staff, will be trained in confidentiality, protection of human subjects, enrollment, randomization, and data collection methods. This person will manage enrollments, randomization, and the 2WT database, including text and voice follow-up communication with intervention clients. Malawi-based co-investigators, including MoH collaborators, will also be invited for Medic Mobile training.

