#### *2WT (intervention):*

All new ART registrants who fill locator forms will be asked to consent to 2WT; those who enroll will receive an enrollment confirmation text, additional texting information, and response instruction at initiation. ART initiates who fail to bring their phone at their first visit or otherwise decide to participate after the initiation visit will be eligible to join the study at any visit within the first 6 months on ART. They will also be asked to consent to 2WT; those who enroll will receive an enrollment confirmation text, additional texting information, and response instruction at enrollment. 2wT paper clients files will be marked to alert reception of participation. Then, 2WT data clerk will manually enter client unique ID, client phone number and scheduled visit dates into 2WT system. Successful SMS receipt is verified by 2WT’s system; failed SMS creates a system report. Based on these inputs, the 2WT system will automatically send varying, weekly adherence

support texts and visit reminders (3 and 1 day before) for 12 months, with opt-out at any time. Clients will be asked to respond to visit reminder messages with a “1=will attend” or “0=no.” A “yes” will trigger, “See you soon!” A “no” will trigger hybrid automated and interactive SMS follow-up where clients can request an appointment date change, report transfers, note other outcome, or request a call. These modifiable, scripted texts between 2wT staff and the client will complete ART outcome data (transfer, stop, etc.) or determine the next steps (**Figure 2** for mock-up).

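### A single printed block size of 10, with open allocation and local envelopes, lets up to one assignment in six be known in advance, depending on who sees whole blocks

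*Combined protocol and SAP*

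**What the plan says.** The Randomization section states that participants will be allocated 1:1 to the two arms "using a randomized block design in groups of 10". No other block size is given, and nothing says that the size varies or is withheld from staff. On concealment: "Assignments will be held in opaque envelopes distributed to LH and MPC to meet enrollment pace". The participant opens the envelope: "Site coordinator will be unaware of the envelope's contents until the participant opened and revealed the group assignment to the coordinator". Allocation is then open: "The study design requires that participants and clinic staff are aware of allocation after assignment".

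The Staff training section describes one 2WT study coordinator: "This person will manage enrollments, randomization, and the 2WT database". It also says that all staff at both clinics are briefed on the study protocols, and these contain the block size. Under Consent Procedures, the paragraph on patients has the coordinator confirm eligibility and seek consent.

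The documents do not say whether blocks are specific to a clinic, whether envelopes are sealed or sequentially numbered, or where the list is generated.

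**The concern.** Opaque envelopes opened by the participant protect the envelope in hand. They do not protect the one after it when the block size is fixed and known and every past assignment is visible. Once five clients of one arm have appeared in a block of ten, all remaining places go to the other arm, and anyone keeping a tally knows it.

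The person best placed to keep that tally also enrols, confirms eligibility and takes consent. Consent comes before the envelope, so knowledge of the next arm could act only through whom staff approach or process next. If clients thought likely to stay in care were brought forward when the next place was known to be 2wT, and others when it was known to be control, the retention comparison would be biased. The baseline covariates named under Data analysis (age, sex, WHO stage) would not fully remove selection based on staff judgement.

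**Working it through.** The plan gives no predictability figure to reproduce.

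**Inputs**
- Allocation 1:1 in blocks of 10, so k = 5 per arm (Randomization).
- 410 participants needed, up to 500 enrolled (Sample size calculation: "410 (205 per arm) will be needed, and up to 500 will be enrolled"). That is 410/10 = 41 blocks, or 500/10 = 50.
- Clinic sizes of 24,000 and 11,000 (Background). They are used only as an assumed guide to how enrolment might split: 24/35 = 69% and 11/35 = 31%.
- Steering of ±2 to ±5 points of expected retention on certain places (assumed; the documents give no figure).

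**1. One person sees whole blocks.** This applies with one coordinator overall, or with blocks issued by clinic. Expected certain assignments in a block of 2k = 2k/(k+1) = 10/6 = 1.667, a share of 1/6 = 16.7%. Enumerating all 252 possible blocks agrees: the known run at the end of the block has length 1, 2, 3, 4 or 5 in 55.6%, 27.8%, 11.9%, 4.0% and 0.8% of blocks, with mean 1.667. Over the trial this gives 41 × 1.667 = 68 of 410, or 50 × 1.667 = 83 of 500. Always guessing the arm with more places left is right 65.3% of the time, against 50% by chance.

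**2. One list is shared and each coordinator sees one clinic.** An assignment is certain only if five of one arm have already appeared at that clinic within the block. By simulation, with the observer still knowing the block boundaries:

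| Share of enrolment seen | Certain assignments |
|---|---|
| 50% | about 0.5% |
| 69% (larger clinic) | about 2.5% |
| 31% (smaller clinic) | about 0.05% |

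**3. Effect on the retention difference.** Suppose a share s of places in each arm is certain, and clients placed there are better by v points in one arm and worse by v in the other. The difference then moves by 2 × s × v.
- Whole blocks, v = 2: 2 × 0.167 × 2 = 0.7 points.
- Whole blocks, v = 5: 2 × 0.167 × 5 = 1.7 points.
- Shared list split 50:50, v = 5: 2 × 0.005 × 5 = 0.05 points.

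**4. Randomly varied sizes 8, 10, 12 and 14.** A simulation of 410 assignments, with an observer who sees every one and knows the set of sizes but not their order, gives about 0.6% certain and best-guess accuracy of about 65%.

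**The case against.** The strongest objection is that the one-in-six figure rests on a premise that the documents do not establish. Staff training describes one coordinator, but Randomization speaks of a site coordinator with envelopes sent to two clinics. Protection Against Risk also refers to a site coordinator, and the recruitment text allows teams or clinicians to enrol. With a shared list and one clinic in view, the figure falls to about 2.5% or less. This stands, and the figure must be stated as conditional.

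A reader might also infer that the coordinator controls timing, because some clients are "eligible to join the study at any visit within the first 6 months on ART". The 2WT (intervention) section gives that flexibility to clients who came without a phone or decided later. It does not let the coordinator defer a willing client. What remains is informal leeway over whom to approach or process next, and that is inferred rather than written.

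The size is modest too. Even 1.7 points requires every certain place to be steered, always in the same direction. It is about one-ninth of the gain from 67% to 82% discussed under Limitations (1.7/15 = 0.11). Nor is 10 a poor number in itself: fixed blocks of 6 or 4 would make 1/4 or 1/3 of assignments certain. Finally, varied sizes barely change best-guess accuracy. All of this is correct.

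It does not remove the point. Whole-block visibility is one natural reading of the plan, nothing written rules it out, and consent before a participant-opened envelope does not prevent counting.

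**Conclusion.** The concern holds as a conditional weakness in allocation concealment. If one person sees whole blocks and knows their size and boundaries, 16.7% of assignments (about 68 of 410) are certain in advance. If one list is shared and each coordinator sees one clinic, the share is about 0.5% at an even split, or about 2.5% and 0.05% at the larger and smaller clinic if enrolment follows clinic size (assumed). The documents do not settle which applies.

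The possible shift in the retention difference is about 0.7 to 1.7 points in the whole-block case and about 0.05 points or less under an evenly split shared list. Both rest on assumed steering of every certain place. A reader might take the design to show that selection bias has occurred or will occur. The documents show only the opportunity. The weakness is worth correcting because the remedy is cheap and the trial was requested to supply more rigorous evidence.

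**What to change.** In the Randomization section, replace the fixed groups of 10 with computer-generated permuted blocks of randomly varied size (for example 8, 10, 12 and 14). Use a separate list for each clinic, generated away from the clinics. Keep the sizes out of the protocol and site documents. State that envelopes are opaque, sealed and sequentially numbered. The separate lists should come with the varied sizes: clinic lists with a fixed block of 10 would make the 16.7% case certain to apply.

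This cuts certain assignments to about 0.6% even if the set of sizes leaks out. It removes certainty, not all predictability, since best-guess accuracy stays near 65%.

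The cost is a regenerated list and a short text edit, with no added staff or participants. Arm sizes may be slightly less balanced at an interim look: the largest possible imbalance inside an unfinished block is half its size, so 7 for a block of 14 against 5 for a block of 10, on each list. If envelopes have already been issued, change those that remain and report the scheme actually used.

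### Receipt of the confirmation text is an eligibility criterion, but it is checked after the arm is revealed, and those who fail are withdrawn and replaced with no rule keeping them in the analysis

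*Combined protocol and SAP*

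**What the plan says.** In the Participant eligibility section, the list introduced by "2WT-specific eligibility criteria for all clients are" has as item 6: "receives confirmed 2WT enrollment text to verify enrollment number". The Randomization section opens consistently with that: "After routine recruitment consistent with 2wT procedures, eligibility, and informed consent, 410 2wT-eligible participants will be randomized 1:1 intervention and control".

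The same section then describes a different order. The participant opens the envelope and shows the arm to the site coordinator. Next, "Coordinator then enters participant group assignment as part of 2wT enrolment, confirming phone number as is routine". Finally, "Those who do not receive the confirmation text while in clinic will be immediately withdrawn and replaced". The section also states that participants and clinic staff know the allocation once it is made.

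The Sample size calculation section plans for these removals. Enrolment may rise from 410 to 500 "to allow for buffer and withdrawal of those with lack of SMS confirmation receipt", and it says that such cases are documented. The Data analysis section names tests and models and compares the arms at 6 months. It defines no analysis population, contains no intention-to-treat statement, and gives no rule or sensitivity analysis for participants withdrawn for this reason.

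**The concern.** A criterion that defines who may enter the trial is tested after allocation, by people who know the arm, and failing it removes the person and brings in a replacement. The groups analysed are then not the groups randomised.

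The consequence depends on whether controls are also sent the text at baseline. If only the 2wT arm is screened, that arm loses clients with non-working numbers and the control arm keeps them. Such clients could well have worse recorded retention: B2C tracing starts by phone, and a client-reported transfer counts as retained. The 2wT arm would then look better with no real effect. If both arms are screened identically, the exclusion mainly narrows the population. A reader cannot tell from the plan which case applies. Every outcome compared between arms is affected.

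**Working it through.** **Order of steps.** By the opening sentence of Randomization: consent, eligibility (including the text), randomisation. By the steps that follow in that section: envelope opened, arm revealed, arm entered and number confirmed, text received or not, withdrawal and replacement. The two orders cannot both hold. How a replacement takes an envelope within the blocks of 10 is not stated.

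**Are controls texted at baseline?**
- Suggesting not: the text is described under the 2WT (intervention) heading ("those who enroll will receive an enrollment confirmation text, additional texting information, and response instruction at initiation"), and item 11 of the numbered RCT procedures enrols controls into 2wT only at 6 months.
- Suggesting so: the criteria are set for all clients, every assignment is entered as part of 2wT enrolment, and the Overall approach section adds an arm field to the 2wT software.

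The documents leave this open.

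**Inputs from the plan.** 205 per arm; up to 500 enrolled against 410 needed, so 500 − 410 = 90 extra and 90/500 = 18%. This is a ceiling over both arms, since the 90 also serve as general buffer.

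**Assumptions (not in the documents).** No true effect; 20% attrition overall; a share q removed; attrition among those removed k times that among those kept; 205 analysed per arm; removal in the 2wT arm only unless stated.

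**Formulas.** From 0.20 = (1 − q)p + qkp, attrition among those kept is p = 0.20/(1 − q + kq). With d = 0.20 − p and p̄ the mean of the two proportions, SE0 = √(2p̄(1 − p̄)/205) and SE1 = √(p(1 − p)/205 + 0.20 × 0.80/205). The two-sided 5% rejection rate is Φ((d − 1.96·SE0)/SE1) + Φ((−d − 1.96·SE0)/SE1).

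**Example, q = 0.10, k = 2.** p = 0.20/1.10 = 0.1818; d = 0.0182; SE0 and SE1 are both 0.0388. Rate = Φ(−1.49) + Φ(−2.43) = 0.068 + 0.008 = 7.5%.

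| k | Removed from 2wT arm | Attrition, 2wT v control | False-positive rate |
|---|---|---|---|
| 2 | 5% | 19.0% v 20.0% | 5.7% |
| 2 | 10% | 18.2% v 20.0% | 7.5% |
| 2 | 18% | 16.9% v 20.0% | 12.5% |
| 2 | 90/295 = 30.5% (whole buffer in one arm) | 15.3% v 20.0% | 23.6% |
| 1.5 | 5% | 19.5% v 20.0% | 5.2% |
| 1.5 | 10% | 19.0% v 20.0% | 5.7% |
| 1.5 | 18% | 18.3% v 20.0% | 7.1% |

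A simulation of 1,000,000 trials for the k = 2 rows gives 5.6%, 7.4%, 12.3% and 23.4%.

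**Cases with little or no bias.** With k = 1, or the same q and k in both arms, the two proportions are equal and the rate is 5%. With both arms checked but 10% of 2wT and 5% of control removed (k = 2), attrition is 0.20/1.10 = 18.2% v 0.20/1.05 = 19.0%, and the rate is 5.6%.

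**The case against.** The strongest reply is that the bias needs one-sided screening, which the documents do not establish. The reading that both arms are texted has real support, and on it the expected bias is about zero. The table of activities that differ by arm does not list the confirmation text. Receipt is verified by the system ("failed SMS creates a system report"), withdrawal happens before any outcome, and the cases are documented. The requirements of own phone and willingness to text should keep failures few, and at 5% removed the error rate barely moves.

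Much of this is fair. The larger error rates do need one-sided removal of 10% or more together with clearly worse attrition, and the 30.5% row is an extreme. By-arm reporting would be feasible from records already planned.

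Two things are not answered. Documenting withdrawals does not keep those people in the analysis, and by-arm reporting is not promised. Nor does system verification remove all judgement: the rule turns on receipt while in clinic, with no waiting time or number of attempts given, and it is applied with the arm known. That the harmless reading is possible but unstated is itself a reason to correct the text.

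**Conclusion.** The concern holds and must be fixed. The Randomization section contradicts its own stated order and removes randomised participants after the arm is known, and nothing in the Data analysis section keeps them.

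The size cannot be fixed from the documents, because neither the SMS failure rate nor the attrition of those who fail is given. Under one-sided screening and the assumptions above, the spurious gain in retention at twice the attrition is 1.0, 1.8 or 3.1 percentage points for 5%, 10% or 18% removed, with the false-positive rate rising from 5% to between 5.7% and 12.5%. It is smaller at 1.5 times the attrition and nil under identical screening of both arms. The severity rests on the break in the randomised comparison, which analysis cannot fully repair if withdrawn participants are not followed, and on how easily it can be avoided. It does not rest on any single figure.

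**What to change.** After consent, send the confirmation text, or one neutral test SMS if the software cannot send it before an arm is entered, to every candidate. Confirm receipt before the next envelope is opened. Replace the sentence on withdrawal and replacement with:

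*No participant is withdrawn by staff or replaced for SMS failure after the envelope is opened; all randomised participants are analysed in their assigned arm, and SMS failures are reported by arm.*

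State whether controls are sent the text at baseline. Say also that the analysis rule covers, alike in both arms, any randomised client who does not go on to start ART, since starting ART is itself criterion 7. A participant's own right to withdraw is unaffected.

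**Cost.** A reordered step in the enrolment SOP, two or three protocol sentences and, if controls are not now texted, about 205 extra messages. Numbers that stop working after randomisation will dilute the effect slightly. The plan gives its control hazard of 0.2 no time unit. Taking it over 6 months, attrition is 1 − exp(−0.2) = 18.1% in controls and 1 − exp(−0.2 × 0.41) = 7.9% with 2wT. If 0%, 2% or 5% of the 2wT arm stay at the control rate, two-proportion power at 205 per arm is 87.3%, 85.7% or 83.1%.

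Keeping everyone without moving the check would cost more if failures are common. With 20% v 8.2% attrition (0.20 × 0.41) and no benefit in those who fail, power at 205 per arm is 93%, 90%, 86% and 78% for 0%, 5%, 10% and 18% failing. Moving the check ahead of the envelope is therefore the main change.
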